### 8.2. Setting

The source population for this study will be the subset of patients contributing data to the GloBE-Reg registry who are treated with either long acting Ngenla (somatrogon) or daily hGH Genotropin (somatropin) at the discretion of the prescribing physician. This population is thought to be a representative sample of children treated with Ngenla (somatrogon) and Genotropin (somatropin) across the world. Data will be included from eligible participants of any age who meet the study criteria and who receive care at centers enrolled in GloBE-Reg that have agreed to share their data with Pfizer during the data collection period. The registry is growing and additional centers around the world are expected to be included over the course of the study period.

The data collection period is from September 30, 2025 to August 31, 2035. No sampling will be performed. Participants can be located anywhere in the world and will be followed up to 10 years until the end of the study or one of the following occurs: withdrawal of consent, discontinuation of

either Ngenla (somatrogon) or Genotropin (somatropin), discontinuation from the GloBE-Reg registry, lost to follow up or death.

The treating physician will follow patients treated with Genotropin (somatropin) or Ngenla (somatrogon) as per routine clinical practice and will collect and enter relevant patient data as part of the defined minimum data set collected by the GloBE-Reg registry.

During the study, duration of treatment exposed will be defined as:

Genotropin/Ngenla: (last dose date – baseline date + 1)/365.25,

where baseline date is the initial visit date on the Reported Outcomes eCRF form.

The data collected via GloBE-Reg will be de-identified and sent to Pfizer for analysis. Pfizer will analyze the data to evaluate treatment effectiveness, safety, adherence and compliance.

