assessment date	exposure	GloBE-Reg data base	Categorical day, month, year
start date of first rhGH therapy	exposure	GloBE-Reg data base	Categorical day, month, year
start date of current rhGH therapy	exposure	GloBE-Reg data base	Categorical day, month, year
Total weekly dose	exposure	GloBE-Reg data base	numerical variable numerical input (1-100)
change in dose since last visit	exposure	GloBE-Reg data base	Categorical yes, no, unknown
Reason for change	exposure	GloBE-Reg data base	Categorical drop down menu or free text – dose adjustment for size, to optimise growth, low IGF-1, high IGF-1, adverse events, other (free text)
Reported missed doses in an average month	exposure	GloBE-Reg data base	Categorical drop down menu – unknown, 1, 2, 3, 4 or 5
Reported missed doses in an average week	exposure	GloBE-Reg data base	Categorical drop down menu – unknown, 1, 2, 3, 4, 5, 6, 7
Therapy stopped	exposure	GloBE-Reg data base	Categorical drop down menu – unknown, not applicable, yes, no

090177e1a57a0182\Approved\Approved On: 16-Feb-2026 13:43 (GMT)

Date of therapy stop	exposure	GloBE-Reg data base	Categorical day, month, year
Reason for therapy stop	exposure	GloBE-Reg data base	Categorical drop down menu – not applicable, unknown, patient choice, poor efficacy, adverse events, final height achieved, other
Reinitiation of rhGH after final adult height	exposure	GloBE-Reg data base	Categorical drop down menu – unknown, not applicable,
Diagnosis			
Visit date	Treatment characteristic	GloBE-Reg database	Categorical Day-month-year
Date of assessment	Treatment characteristic	GloBE-Reg database	Day-month-year
Primary condition			
Primary condition:	Baseline clinical characteristic	GloBE-Reg database	Categorical Drop down menu - Chronic Kidney Disease - type GHD - Non-specific – type Acquired - CNS infection - Extracranial tumor - Intracranial tumor - Granulomatous disease - Other - Radiation therapy - Trauma - Vascular anomaly Congenital

090177e1a57a0182\Approved\Approved On: 16-Feb-2026 13:43 (GMT)

090177e1a57a0182\Approved\Approved On: 16-Feb-2026 13:43 (GMT)

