Exposure scenarios: Medication error	outcome	GloBE-Reg database	Categorical  - Visit date - Date of assessment - Type of medication error (accidental/intentional) - Classification (wrong drug/route/frequency/dose/other) - Date when it occurred - Date when it was reported to physician - Report to authorities details - Adverse events associated with medication error - Other details  See SAP
---	---------	--------------------	---

Baseline date is the initial visit date on the Reported Outcomes eCRF form.

The potential covariates and confounders that will be considered for the models in addition to treatment (Genotropin and Ngenla) are the following baseline variables, classified into different categories:

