**Analysis of the Secondary Endpoints:**

For secondary endpoints, safety events of interest, medication errors and efficacy measurements, descriptive statistics, counts and proportions, crude incidence rates (i.e., number of events per person years) with associated two-sided 95% confidence intervals will be calculated. Incidence rate is calculated as the number of individual events observed during the time at risk (exposure time), divided by the total number of patient-years at risk for the event, multiplied by 100.

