**Repeated Measures**

This model will only be performed with those patients without treatment switch until a given time point. Continuous variables will be analyzed by a Mixed Model for Repeated Measures (MMRM) under the MAR framework, including all post baseline timepoints data as outcome variables and baseline data as a covariate including the relevant patient/disease characteristics. Repeated time variable will be modeled as a continuous variable and treatment (Genotropin versus Ngenla) as a class variable with an unstructured covariance and least square means along with 95% CI will be presented.

The adjusted mean changes from Baseline at Month 6, 12, 18, 24, etc., for each treatment group will be estimated in the framework of this model, as well as the between group differences and the 95% CIs for the adjusted mean, when applicable.

The MMRM model will be implemented using SAS® (version 9.4 or higher) generalized linear mixed procedure (PROC MIXED) with an unstructured correlation matrix to model the within-patient errors. If this model does not converge, a heterogeneous Toeplitz covariance structure followed by the

090177e1a57a0182\Approved\Approved On: 16-Feb-2026 13:43 (GMT)

heterogeneous first-order autoregressive covariance structure will be considered. Parameters will be estimated using the Newton-Raphson algorithm. Denominator degrees of freedom will be estimated using the Kenward-Roger approximation.

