### **Longitudinal Model/Sensitivity Analysis**

To assess the longitudinal association between outcomes and time-varying treatment (*i.e.* patients switch treatment from Genotropin to Ngenla or vice versa at any time-point), a propensity model approach will be applied to calculate the inverse probability of treatment weights (IPTW). This model is assumed to control for time-varying confounding when time-varying treatments are used in longitudinal analyses.

The IPTW will be calculated using propensity score model in which the choice of the treatment at each visit will be considered as the outcome (Genotropin vs Ngenla) and the pre-specified baseline characteristics (See Table 9-3 Model Covariates) as independent variables. Once IPTWs per patient are derived, the models described in the Repeated Measure model will be applied with the weights. The models will include treatment group (time-varying covariate), time (in years) and IPTW. This approach will be considered as a sensitivity analysis *to assess the impact of treatment switching*.

Detailed methodology for summary and statistical analyses of data collected in this study will be documented in a statistical analysis plan (SAP), which will be dated, filed, and maintained by the sponsor. The SAP may modify the plans outlined in the protocol; any major modifications of primary endpoint definitions or their analyses would be reflected in a protocol amendment.

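### Exposure to each drug runs from the baseline visit even when the drug was started later, so incidence rates and the IRR take in time not spent on that drug

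*Protocol*

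**What the plan says.** Section 8.2 (Setting) gives one exposure formula for both products: "Genotropin/Ngenla: (last dose date – baseline date + 1)/365.25". The origin of the clock is defined in the same section and again in section 8.3 (Variables): "Baseline date is the initial visit date on the Reported Outcomes eCRF form". It is one date per patient and is not tied to the start of either drug.

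Section 8.7 (Analysis of the Secondary Endpoints) makes this time the denominator. Events seen while at risk, which the text equates with exposure time, are "divided by the total number of patient-years at risk for the event"; the rate is given per 100 patient-years. The paragraph on count outcomes then estimates an IRR between the two treated groups by Poisson or negative binomial regression. The safety overview (Table 8-7) lists rates and IRRs for SAEs and medication errors.

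The Longitudinal Model paragraph foresees that "patients switch treatment from Genotropin to Ngenla or vice versa at any time-point". The only restriction on switchers concerns the repeated-measures model: "This model will only be performed with those patients without treatment switch until a given time point". No rule divides person-time at a switch for the rates or the IRR. The variables table already collects the "start date of current rhGH therapy" and the date therapy stopped.

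**The concern.** A drug-specific rate needs a denominator made of time on that drug. The formula provides this only if the patient was already taking the drug at the baseline visit and did not change. Otherwise the interval between that visit and the drug's start is credited to a drug the patient was not yet taking. This can happen in three ways: a switch between the study drugs, a change from another growth hormone brand (the registry covers all available forms), or an initial visit before the first dose.

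Incidence rates of safety events are the first secondary objective of a study designated as a PASS. A denominator that mixes drugs affects each drug's rate and the ratio between them.

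**Working it through.** The protocol states no event rate, switch share or time to switch, so there is no planned figure to reproduce. The formula is from section 8.2 and the 700 expected Ngenla patients from section 8.5. All other inputs below are assumptions. Last dose date is read as the last dose of the drug in question.

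**One switcher.** Baseline is day 1, Genotropin runs from day 1 to 1096, and Ngenla from day 1097 to 1827.

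- Genotropin by the formula: (1096 − 1 + 1)/365.25 = 3.00 years.
- Ngenla by the formula: (1827 − 1 + 1)/365.25 = 5.00 years.
- Ngenla from its own start: (1827 − 1097 + 1)/365.25 = 2.00 years.

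The formula gives 3 + 5 = 8 patient-years from 5 calendar years. This patient's Ngenla denominator is 5/2 = 2.5 times too large.

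**A cohort, events assigned to the drug in use.** Each of 700 Ngenla patients has T = 5 years from baseline to last dose, and a share s switched in from Genotropin a years after baseline. Counted time is 700 × T = 3500 patient-years; time truly on Ngenla is 700 × (T − s·a). The computed rate is therefore the true rate times 1 − s·a/T. With equal true rates and no reverse switching, the IRR carries the same factor:

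| Share switched in | a = 1 year | a = 2 years | a = 3 years |
|---|---|---|---|
| 0% | 1.00 | 1.00 | 1.00 |
| 10% | 0.98 | 0.96 | 0.94 |
| 25% | 0.95 | 0.90 | 0.85 |
| 50% | 0.90 | 0.80 | 0.70 |

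For example, at s = 50%, a = 3 and a true rate of 2.0 per 100 patient-years, true time is 700 × 3.5 = 2450 patient-years with 49 events. The computed rate is 100 × 49/3500 = 1.40.

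**The same cohort, events since baseline all carried to Ngenla.** Take s = 50%, a = 2 and a true Ngenla rate of 2.0. Ngenla events: 0.02 × 2800 = 56. Earlier Genotropin time: 700 × 0.5 × 2 = 700 patient-years.

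- Genotropin rate 2: (56 + 14)/3500, or 2.0 per 100.
- Genotropin rate 1: (56 + 7)/3500, or 1.8 per 100.
- Genotropin rate 4: (56 + 28)/3500, or 2.4 per 100.

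The result is a mixture of the two drugs' rates and can lie above or below the Ngenla rate.

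**Reverse switching.** Patients moving from Ngenla to Genotropin inflate the Genotropin denominator in the same way, which pushes the IRR up.

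**The case against.** The strongest objection is the follow-up rule. The abstract (Population) and section 8.2 end follow-up when either study drug is discontinued. Read literally, a Genotropin patient who moves to Ngenla leaves at the switch and contributes 3 Genotropin years and no Ngenla years, so the 8-from-5 count cannot arise. This has weight, but the time-varying switch analysis in section 8.7 needs data after the switch, and the two texts do not agree. The rule also leaves untouched a patient whose initial visit was on another brand or before the first dose. The first inclusion criterion, that participants be receiving a study drug, makes untreated lead-in less likely but does not exclude it.

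A second objection is that section 8.3 leaves operational definitions to the SAP, which may modify the protocol's plans. That is true, but here the protocol itself fixes the formula. It is also fair that the rates are descriptive and secondary, and that with few switchers the distortion is small.

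Three stronger readings are tempting. A reader might infer that all exposure is miscounted. It is not: for patients on the drug at the first visit who never switch, starting at that visit is correct. A reader might infer a bias in favour of Ngenla. The protocol foresees switching in both directions and gives no proportions, and no event-assignment rule is stated, so the direction is not established. A reader might also infer that the effectiveness analyses need a new time zero. The documents do not support that: section 8.7 presents the height outcomes by naive and non-naive status, Table 8-3 lists naive status and duration of treatment as covariates, and the repeated-measures model is restricted to patients without a switch. Some mixing remains in the overall estimates and non-height outcomes, but moving time zero to therapy start could leave patients treated before registry entry without a baseline value.

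**Conclusion.** The point holds for the safety rates and the IRR. For any patient who starts a study drug after the baseline visit, the formula puts time not on that drug into its denominator. For switchers this depends on their being followed past the switch, on which the protocol contradicts itself.

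If events are assigned to the drug in use, the later drug's rate is too low. The IRR range of 0.98-0.70 rests wholly on the assumptions stated: 10-50% of Ngenla patients switching in after 1-3 of 5 years, equal true rates and no reverse switching. If earlier events are carried over, the rate is a mixture with no fixed direction. The actual size and sign cannot be derived from the protocol.

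**What to change.** Replace the formula in section 8.2 with person-time per drug episode:

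- Start at the later of that drug's start date and the baseline visit.
- End at the earliest of that drug's last dose, the switch or the data cut.
- Take (end − start + 1)/365.25 and sum the episodes within patient and drug.
- Assign each event to the drug in use at onset, and state this rule beside the incidence-rate definition in section 8.7.

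Reconcile the end-of-follow-up rule (abstract and section 8.2) with the time-varying switch analysis in section 8.7, so that it is clear whether time after a switch is included. Leave the effectiveness baseline as it is.

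The cost is one revised definition and one added sentence in the protocol, carried into the SAP. The start date of current therapy and the therapy stop date are already registry fields, so no new data collection is needed. Patients on one drug throughout keep the same person-time.

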### 8.2.1. Inclusion Criteria

Participants must meet all the following inclusion criteria to be eligible for inclusion in the study:

1. Receiving treatment with either Ngenla (somatrogon), or Genotropin (somatropin), at the discretion of the prescribing physician.
2. Confirmation of consent to participate in the GloBE-Reg registry and consent to have data shared with Pfizer as part of the PROGRES 2.0 sub-study.

### 8.2.2. Exclusion Criteria

Participants meeting any of the following criteria will not be included in the study:

1. Participation in any interventional clinical trial during the study period
2. Data fails to pass GloBE-Reg quality checks

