## Study size

The study is descriptive in nature without *a priori* hypothesis testing, therefore, a formal sample size estimate is not required. All eligible participants treated will be included. It is expected that at least 2000 Genotropin (somatropin) treated and 700 Ngenla (somatrogon) treated participants will be included in final analysis. The study will be conducted for a total of 10 years.

As of June 30, 2025, the GloBE-Reg registry includes data on 365 participants on treatment with Genotropin (Somatropin) and 157 participants on treatment with Ngenla (somatrogon). Since this is an expanding registry, participant numbers are expected to grow over the study period for both treatment groups.

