### 8.3. Variables

The operational definitions will be included and detailed in the statistical analysis plan (SAP).

Variable	Role	Data Source(s)	Operational Definition
Core			
Study Site ID	Baseline	GloBE-Reg data base	Assessed at baseline
Demographics			
Date of birth	Baseline demographic	GloBE-Reg data base	Categorical month, day, year
Participant follow-up status	exposure	GloBE-Reg data base	Categorical Patient active, inactive, care suspended, care

			terminated, deceased, unknown
Date of death	outcome	GloBE-Reg data base	Categorical Month, day, year
Primary cause of death	outcome	GloBE-Reg data base	Categorical: See SAP
Sex at birth	Baseline characteristic	GloBE-Reg data base	Categorical male, female, other, unknown
Current gender	Baseline characteristic	GloBE-Reg data base	Categorical Male, female, non-binary, other, asked but unknown, unknown, same as sex at birth
Country at birth	Baseline demographic	GloBE-Reg data base	Categorical Select from any country in the world
Country of usual residence	Baseline demographic	GloBE-Reg data base	Categorical Select from any country in the world
Other			
Consent for PRO collection	Baseline	GloBE-Reg database	Categorical Yes, no, unknown
Participation in other registries (PROGRES 1.0)	Baseline demographic	GloBE-Reg data base	Categorical Yes, no, unknown
Name of registries (PROGRES 1.0 only)	Baseline demographic	GloBE-Reg data base	Free text box
Registry participant ID(s) (PROGRES 1.0 only)	Baseline demographic	GloBE-Reg data base	Free text box

090177e1a57a0182\Approved\Approved On: 16-Feb-2026 13:43 (GMT)

Treatments			
Drug group and sub-group	exposure	GloBE-Reg data base	Categorical drug
Commercial name of drug used	Treatment characteristic	GloBE-Reg data base	Categorical LAGH,dGH, Somatrogon, Genotropin
Drug Indication			
Drug indication type	Treatment characteristic	GloBE-Reg data base	Categorical
Drug indication:	Treatment characteristic	GloBE-Reg data base	Categorical  Drop down menu – select from indication options listed  Drug indication:  - Chronic Kidney Disease - Growth Hormone Deficiency (GHD)-type- Idiopathic short stature - Noonan syndrome - Prader Willi Syndrome - Skeletal Dysplasia – type - Small for Gestational Age (SGA) - type - Turner Syndrome - Other Disorder - type
hGH exposure			
visit date	exposure	GloBE-Reg data base	Categorical day, month, year

090177e1a57a0182\Approved\Approved On: 16-Feb-2026 13:43 (GMT)

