## 8.5. Study Size

The study is descriptive in nature without any *a priori* hypothesis testing; therefore, a formal sample size estimate is not required. All eligible participants treated will be included. It is expected that at least 2000 Genotropin (somatropin) treated and 700 Ngenla (somatrogon) treated participants will be included in the final analysis.

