## 8.6. Data Management

All data for this study will be collected through the routine data collection practices of the GloBE-Reg registry. Investigators in each country will independently generate the data needed for the registry. The investigators will check the data for consistency in terms of range of values, units of measurement, and relevance of clinical information.

The registry is a web-based interface linked to a secure database at the University of Glasgow, and investigators at centers around the world add pseudonymized, routinely collected clinical data on patients who provide consent to participate in the registry. Data contained in other databases and registries can also be uploaded using a bulk transfer method, which avoids manual double entry through bulk upload of core and longitudinal data.

All participant data is stored by GloBE-Reg on a secure physical server at the University of Glasgow, which is managed and reviewed by Central IT Services. Additional details can be found in University of Glasgow's Data Protection Impact Assessment (DPIA) document (Annex 1).

Data for participants treated with Ngenla (somatrogon) and Genotropin (somatropin) will be provided to Pfizer only after centers provide consent to share their data. Data transferred to Pfizer will be in CSV format every 6 months using CONFORM 4.0.10 or later via secure file transfer protocol and stored internally on a secured dedicated server. The data will be converted to SAS format for analysis and reporting and will be processed by Pfizer to create analytical variables and datasets for all analyses specified in the study protocol. All study data will exist as structured data by the start of the study. The data analysis and results generation will strictly follow the approved SAP. If for any reason any statistical method needs to be carried out differently than described in the SAP, an amendment to the SAP with required documentation and new approval will be done. All computations and generation of Tables, Listings and Data for figures will be performed using SAS Version 9.4 or higher.

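### The trial-participation exclusion has no baseline anchor, so a participant who joins an interventional trial late in the study loses all earlier valid follow-up

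*Protocol*

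**What the plan says.** Section 8.2.2 opens with "Participants meeting any of the following criteria will not be included in the study" and gives as its first criterion "Participation in any interventional clinical trial during the study period". The consequence is that the person is left out, and no time point is attached to the criterion.

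Section 8.2 states: "The data collection period is from September 30, 2025 to August 31, 2035". The abstract adds, under Study size, "The study will be conducted for a total of 10 years". Participants "will be followed up to 10 years until the end of the study or one of the following occurs: withdrawal of consent, discontinuation of" either product, leaving the registry, loss to follow-up or death. The Population paragraph of the abstract gives the same list. Starting an interventional trial is in neither.

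Data reach the sponsor repeatedly (Section 8.6: "Data transferred to Pfizer will be in CSV format every 6 months"), and Section 8.7 says that everything received from the registry is analysed. The variables table in Section 8.3 records participation in other registries but has no flag or date for an interventional trial. The limitations in Section 8.9 do not mention selection by later trial entry.

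**The concern.** Eligibility for a cohort should be decidable from what is known at baseline. Here it can change at any point in nearly ten years. A participant with several years of sound follow-up becomes ineligible on joining a trial, and no rule in the protocol keeps the earlier data.

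Two results are exposed. In the effectiveness comparison, if participants with a poor response are more likely to enter trials, their earlier heights and IGF-I values leave the analysis, possibly to a different degree for each product. In the safety analysis, the criterion covers any trial, including one that treats an adverse event. Leukaemia and neoplasm are listed outcomes in Section 8.3. A participant who develops one and then enters a trial for it would be removed together with the event and the patient-years. Section 8.7 defines the incidence rate as events over patient-years at risk, so an event could leave the numerator because of what it led to.

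**Working it through.** The protocol states no figure that depends on this point, so there is nothing to reproduce. The check sets the rules side by side and then illustrates the size under stated assumptions.

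**Step 1: length of exposure to the rule.** 30 September 2025 to 31 August 2035 is 3,622 days; 3,622 / 365.25 = 9.92 years.

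**Step 2: follow one participant through the rules.** Take someone with six valid years of follow-up who then joins a trial.

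- Section 8.2.2: the criterion is met, so the participant is not included.
- Section 8.2: trial entry does not end follow-up, so nothing preserves the six years.
- Sections 8.6 and 8.7: the six years have already been transferred in half-yearly files, and all data received are to be analysed.

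The first and third rules conflict for this participant, and the second does not settle it.

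**Step 3: size under assumed rates.** The protocol gives no rate of trial entry. Assume a constant yearly rate h and T years of potential follow-up per participant.

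- Share of participants excluded = 1 − exp(−hT)
- Valid person-years per participant if censored at entry = (1 − exp(−hT)) / h
- Person-years per participant kept under whole-person exclusion = T·exp(−hT)
- Share of valid person-time discarded = 1 − kept / valid

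Example, h = 1% and T = 10: excluded 1 − exp(−0.1) = 9.5%; valid 0.0952 / 0.01 = 9.52; kept 10 × 0.9048 = 9.05; discarded 1 − 9.05 / 9.52 = 4.9%.

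| T (years) | h per year | Excluded | Valid years | Kept years | Person-time discarded |
|---|---|---|---|---|---|
| 10 | 0.5% | 4.9% | 9.75 | 9.51 | 2.5% |
| 10 | 1% | 9.5% | 9.52 | 9.05 | 4.9% |
| 10 | 2% | 18.1% | 9.06 | 8.19 | 9.7% |
| 10 | 3% | 25.9% | 8.64 | 7.41 | 14.3% |
| 4 | 0.5% | 2.0% | 3.96 | 3.92 | 1.0% |
| 4 | 1% | 3.9% | 3.92 | 3.84 | 2.0% |
| 4 | 2% | 7.7% | 3.84 | 3.69 | 3.9% |
| 4 | 3% | 11.3% | 3.77 | 3.55 | 5.9% |

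The 10-year rows are an upper case. The abstract reports 365 Genotropin and 157 Ngenla participants in the registry at 30 June 2025, so most of the expected participants would join later and have less follow-up.

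**Step 4: what selective entry could do.** Assume that 30% of participants are poor responders who join trials at three times the rate h of the others, over 10 years. Their share in the analysed cohort is 0.30·exp(−3hT) / [0.30·exp(−3hT) + 0.70·exp(−hT)].

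- h = 1%: 0.30 × 0.741 / (0.30 × 0.741 + 0.70 × 0.905) = 26%
- h = 2%: 0.30 × 0.549 / (0.30 × 0.549 + 0.70 × 0.819) = 22%

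If entry is unrelated to outcome and product, the rule costs precision but does not shift the comparison.

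**The case against.** The best defence is that the study period is not formally defined, so the criterion may mean only that a participant must not be in a trial while contributing data. That reading is possible. It still needs different wording, because the present text removes the person and not the time spent in the trial. Calling the study retrospective does not help either, since follow-up accrues to 2035. Nor can this be left to the statistical analysis plan: a plan that kept pre-trial data would contradict Section 8.2.2.

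Several stronger readings are tempting, and the documents do not support them.

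- **A head count of losses.** A reader might apply an assumed percentage to the 2,000 and 700. Section 8.5 expects that "at least 2000 Genotropin (somatropin) treated and 700 Ngenla (somatrogon) treated participants will be included in the final analysis", so these numbers are already net of exclusions and are the wrong base.
- **Bias as an established fact.** Nothing in the protocol shows that trial entry is related to response, diagnosis, centre or product. It is an assumption, and the direction is unknown.
- **Exclusion as the only mechanism.** Discontinuing the product already ends follow-up, so a participant who stops it to enter another growth hormone trial meets both rules. The protocol does not say which takes precedence.
- **Participants vanishing between successive reports.** The milestones list only a final report. Half-yearly transfers and annual investigator meetings make shifting counts possible, but no series of reports is planned.
- **Censoring as a complete cure.** If entry depends on response, censoring at entry is itself informative. The mixed model assumes data missing at random and may absorb part of this; crude incidence rates have no such protection.

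**Conclusion.** The point holds as a fault in a stated rule. As worded, Section 8.2.2 makes inclusion depend on a post-baseline event and discards valid earlier follow-up and events, and it conflicts with the instruction in Section 8.7 to analyse all data received. Both conclusions follow from the text alone, taking the study period to run to the end of data collection.

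The size cannot be established from the protocol. The shares in the table rest on an assumed constant entry rate and on equal potential follow-up for everyone. Bias, as opposed to lost precision, requires the further assumption that entry is related to outcome or product. For rare safety events the loss can be sharp even at a low entry rate: removing one of k events lowers the rate by about 1/k. The rule should be corrected before eligibility is applied to accumulating data.

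**What to change.** In Section 8.2.2, limit the criterion to participants who are in an interventional trial at baseline. In Section 8.2 and in the Population paragraph of the abstract, add the start of an interventional trial to the events that end follow-up. State that data and events up to that date are kept and that the participant is censored there. State also which rule applies when product discontinuation and trial entry coincide, and bring the sentence in Section 8.7 on analysing all received data into line. Add a line to Section 8.9 saying that censoring at trial entry may be informative.

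The text change is a few sentences. The real cost is the date of trial entry: the variables table lists neither a flag nor a date, so it must be obtained from the sites or added as a registry field. Applying the present criterion already requires knowing that a participant joined a trial, but not when. The change keeps earlier person-time and events and so reduces the selection; it does not remove every source of bias.
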